86 **glargine once daily plus aspart insulin before meals.** We will analyze a total of 180 subjects
87 with T2D treated prior to admission with diet, oral hypoglycemic agents, short-acting GLP1-RA
88 (except long-acting exenatide, dulaglutide and albiglutide), or insulin therapy (except degludec
89 and glargine U300) will be included in this prospective, randomized, open label trial to compare
90 the safety and efficacy of a basal bolus regimen with degludec and glargine in patients with T2D
91 admitted to general medicine and surgery services. Secondary end points include length of stay,
92 hospital complications, and hospital readmissions.

93
94 **Objective 2: To determine differences in glycemic control after hospital discharge between**
95 **treatment with degludec and glargine in medicine and surgery patients T2D.** Patients with
96 poorly controlled diabetes (HbA1c $\geq 7.0\%$) enrolled in Aim 1 will be invited to participate in this
97 open label prospective outpatient study. At hospital discharge, patients will be treated following
98 an HbA1c based algorithm²⁴ for a total duration of the outpatient follow-up of 3 months (see
99 hospital discharge algorithm, page 7).

100

101 **III. RESEARCH DESIGN AND METHODS**

102 **III.A Study Hypothesis (hypotheses):**

103 **Hypothesis #1:** Treatment with degludec and glargine will result in equivalent glycemic control
104 in general medicine and surgery patients with T2D. Degludec will result in lower number of
105 hypoglycemia compared to glargine.

106
107 **Hypothesis:** treatment with degludec and glargine will result in a similar improvement in HbA1c
108 levels after hospital discharge. Degludec will result in lower number of hypoglycemia compared
109 to glargine.

110

111 **III.B Endpoints:**

112 **The primary endpoint** of the trial is non-inferiority in mean differences between treatment groups
113 in their mean blood glucose concentrations during the first 10 days of therapy (non-inferiority
114 will be determined at a difference < 18 mg/dl). All participants who receive ≥ 2 doses of study
115 drug will be included in the analysis.

116

117 **Secondary outcomes** include differences between treatment groups in any of the following
118 measures: Endpoints 1-4 (glycemic control) will be analyzed during the first 10 days of therapy
119 and endpoints 5, 7, 8, and 9 (length of stay and complications) will be analyzed during hospital

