255 hypoglycemia: decrease TDD (basal and prandial) insulin dose by 10% every day

- 256 ▪ If a patient develops hypoglycemia (BG <70 mg/dL), the insulin TDD (basal and
- 257 prandial) should be decreased by 20%.
- 258 ▪ If a patient develops severe hypoglycemia (BG <40 mg/dL), the insulin TDD (basal
- 259 and prandial) should be decreased by 30-40%.
- 260 *Consider adjusting prandial dose according to medical discretion

261

262 **Aim 2: Outpatient (Post-Discharge) Arm: To determine differences in glycemic control**

263 **after hospital discharge between treatment with degludec and glargine in medicine and**

264 **surgery patients T2D.** We will compare the efficacy and safety of degludec and glargine after

265 hospital discharge. Several outpatient insulin trials have shown that treatment with degludec

266 results in similar improvement in glycemic control ^{19,20,28}, but in significant reduction in

267 hypoglycemia. We expect that degludec treatment will be a safer alternative to current use of

268 glargine U100 formulation.

269

270 **Insulin Discharge algorithm:**

271 Patients with poorly controlled diabetes (HbA1c ≥7.0 %) enrolled in Aim 1 will be invited to

272 participate in this open label prospective outpatient study. The total duration of the study is 3

[figure not shown]
273 months. Patients with an HbA1c between 7.0% and 10% will be discharged on preadmission oral

274 antidiabetic agents plus degludec or glargine once daily. Patients with an admission A1C ≥ 10%

275 will be discharged on basal bolus regimen with degludec or glargine and aspart insulin before

276 meals. Participants will be trained in using each devices including how to differentiate these

277 from each other (rapid acting from long acting insulin).

279

280 **If previous basal bolus only therapy and/or contraindications to previous oral therapy,

281 discharge on basal bolus at 100% of daily hospital dose.

282

283 **Follow-up Care:**

- 284 • Provide degludec or glargine 1 or 2months supply at each clinic visit.

- 285 • A member of the diabetes research team will contact patients via telephone call every 2
- 286 weeks for a total of 3 months.
- 287 • Patients will be asked to attend outpatient visits at 4 and 12 weeks after hospital
- 288 discharge.
- 289 • Recommendation on insulin adjustment to be provided after each telephone contact
- 290 and/or clinic visit by research staff under supervision of research licensed healthcare
- 291 professional.

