- 292 • Research staff will follow the algorithm for outpatient insulin dose adjustment according
- 293 to fasting blood glucose levels (FBG) and/or random blood glucose levels (RBG)
- 294 described below (algorithm for primary care physician).
- 295

296 **During follow up we will collect the following information:**

- 297 1. Glycemic control:
 - 298 a. Mean daily fasting and premeal blood glucose levels
 - 299 b. HBA1C at 1 and 3 months after hospital discharge
 - 300 c. Hypoglycemic events
 - 301 i. A glucose alert value of <70mg/dl.
 - 302 ii. Clinically important hypoglycemia (BG < 54 mg/dl)
 - 303 iii. Severe hypoglycemia, as defined by the ADA, which denotes severe
 - 304 cognitive impairment requiring external assistance for recovery
 - 305 d. Hyperglycemic events (BG > 240 mg/dl)
- 306
- 307 2. Diabetes treatment:
 - 308 a. Number of patients receiving insulin
 - 309 b. Insulin dosage (unit/day)
 - 310 c. Use of oral agents
 - 311 d. Protocol adherence
- 312 3. Clinical Outcome:
 - 313 a. Hospital readmissions
 - 314 b. Emergency room visits
 - 315 c. Postoperative complications
- 316
- 317 4. Management after end of study
 - 318 a. Post treatment telephone call (telephone contact 2 weeks after last clinic visit) to
 - 319 confirm appropriate number of refills and follow up with primary care physician
 - 320 b. Collect information on adverse events post treatment
- 321

322 **Primary care physicians will be provided with the following algorithm for outpatient**
323 **insulin dose adjustment according to fasting blood glucose levels (FBG) or random blood**
324 **glucose levels (RBG)**

Basal Insulin (degludec and glargine)	
If mean FBG > 180 mg/dL for the last 3 consecutive days and no hypoglycemia or no random BG (RBG) <70 mg/dL	Increase daily dose by 4 IU
If mean FBG > 140 mg/dL for the last 3 consecutive days and no hypoglycemia < or	Increase daily dose by 2 IU

no RBG <70 mg/dL	
If mean FBG between 100 – 140 mg/dL and no hypoglycemia or no RBG <70 mg/dL	No Change
If any FBG between 70 – 99 mg/dl	Decrease by 4 IU or 10% of total daily dose
If any FBG or RBG 40- 69 mg/dl	Decrease by 8 IU or 20% of total daily dose
If any FBG or RBG < 40 mg/dl	Decrease total daily dose by 30 – 40%

325
326 For patients discharged on basal bolus, prandial insulin will be adjusted according to
327 postprandial blood glucose levels (PPG) measured 2 hours after the start of the meal.
328

Prandial Insulin (rapid acting insulin)	
PPG < 180	No change

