434 groups will be treated with bolus regimen given half of TDD as basal (degludec or glargine) once
435 daily and half as aspart divided in three equal doses before meals. Patients with poor oral intake
436 or to be kept NPO will receive the basal dose, but prandial dose will be held.¹⁴ Insulin dose will
437 be adjusted daily to maintain a fasting and pre-dinner BG between 80 mg/dl and 180 mg/dl.

439 **Aim 1. Inpatient Arm – Flow Chart**

440

Visit Type	Hosp- Day 1	Hosp- Day 2	Hosp- Day 3	Hosp- Day 4	Hosp- Day 5	Hosp- Day 6	Hosp- Day 7	Hosp- Day 8	Hosp- Day 9	Hosp- Day 10
Visit #	1	2	3	4	5	6	7	8	9	10
Time-days	1	2	3	4	5	6	7	8	9	10
Inf. consent	x									
Inclusion/excl criteria	x									
Randomization	x									
Withdrawal criteria	x	x	x	x	x	x	x	x	x	x
Dose adjustment		x	x	x	x	x	x	x	x	x
Efficacy										
Vital signs	x									x
Phys Exam	x									x
Body weight	x									x

BMI	x									
HbA1c ¹	x									
Fasting BG		x	x	x	x	x	x	x	x	x
Pre-meal BG	x	x	x	x	x	x	x	x	x	x
Safety										
Adv events	x	x	x	x	x	x	x	x	x	x
Hypoglycemia	x	x	x	x	x	x	x	x	x	x
Urine pregnancy test	x									
Trial material										
Drug dispense ²	x									

441 ¹ From medical records if < 3months, order it otherwise after subject has provided consent for study
442 participation.

443 ² As needed

444 **Aim 2. Outpatient Arm – Flow Chart**

445

Visit Type	Discharge Day 1	TC	Clinic visit	TC	TC	TC	Clinic visit	post treatment follow-up
Visit #	1	2	3	4	5	6	7	8
Time-wks ¹	0	2	4	6	8	10	12	14
Inf. consent	x							
Incl/excl criteria	x							
Random	x							
Withdrawal criteria		x	x	x	x	x	x	
Drug Compliance		x	x	x	x	x	x	
Dose adjustment		x	x	x	x	x	x	
Efficacy								
Vital signs	x		x				x	
Phys Exam	x		x				x	
Body wgt	x		x				x	
BMI	x		x				x	
HbA1c			x				x	
Fasting BG	x		x				x	
Safety								
Adv events	x	x	x	x	x	x	x	x
Hypoglycemia	x	x	x	x	x	x	x	x
Urine pregnancy test			x					
Chem, GFR	x		x				x	
Trial material								
Drug dispense	x		x					
Drug account	x		x				x	

446 ¹Telephone calls (TC) and outpatient visits can be completed ±7 days

447

448

449

450 **Assessments for Efficacy**

451 Laboratory measurements will be conducted per standard hospital practices. Samples will be
452 collected and labelled at the clinical research center at each individual institution. Samples will
453 not be stored. Clinical research coordinators and research nurses will obtain data and blood
454 samples to be sent to the central lab at each institution for standard measurements (HbA1c,

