550 achieve >80% power.

551
552 **Analysis of Primary Endpoint:** The primary endpoint in this study is glycemic control
553 measured by mean daily BG concentration after hospital discharge. Secondary outcomes include
554 rate of hypoglycemia during follow-up, change in HbA1c, body weight, number of episodes of
555 severe hyperglycemia, complications and emergency room visits or hospital readmissions at 12
556 weeks post-discharge. To analyze these outcomes, we will follow the same analytic strategy
557 proposed for the secondary endpoints of Aim 1. We will first compare the primary outcome
558 using two-sample t-tests (or Wilcoxon tests) or one-way ANOVA, followed by multivariate
559 linear regression to estimate and test the difference between the two treatment groups while
560 simultaneously accounting for other potential confounders. Transformations will be applied if
561 normality violation is detected. Stepwise, backward, or forward model selection strategy will be
562 adopted to determine the variables to be included in the final model. Standard diagnostic and
563 model checking procedures will be applied to examine the fit of the developed models.
564

565 **VII. DATA HANDLING AND RECORD KEEPING:**

566 Data collection records with personal identifiers will be stored in locked file cabinets. Blood
567 samples drawn in conjunction with this study will not be labeled with information that could
568 directly identify study subjects. Blood samples will be not be stored. Presentation of the study
569 results at regional or scientific meetings or in publications will not identify subjects. Access to
570 research and confidential records will be limited to clinical investigators, research coordinators,
571 and the IRB at Emory University.
572

573 **VIII. ETHICS:**

574 **Informed Consent.**

575 After identification of eligible patients these individuals will be provided basic information
576 regarding the study and, if interested, a member of the research staff using inclusion/exclusion
577 criteria delineated elsewhere in the protocol will then screen patients. Informed consent will be
578 obtained before any trial related procedures including screening procedures. The consent form,
579 potential risks and benefits, and the rights of research participants will be explained to the
580 participant by the investigators or research coordinator. Individuals will be asked if they have

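### The baseline for the Aim 2 change in HbA1c is undefined and may be a chart value up to 3 months old; this adds noise to a secondary comparison and blurs each arm's own improvement, without biasing the randomized contrast in expectation

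*Combined protocol and SAP*

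**What the plan says.** - **Source of the baseline.** The Aim 1 flow chart (section V) marks HbA1c on hospital Day 1 only. Its footnote 1 reads "From medical records if < 3months, order it otherwise after subject has provided consent for study" participation.
- **Later measurements.** The follow-up list in section III.C gives "HBA1C at 1 and 3 months after hospital discharge". The Aim 2 flow chart agrees: weeks 4 and 12 are marked and the discharge column is blank.
- **Entry to Aim 2.** "Patients with poorly controlled diabetes (HbA1c ≥7.0 %) enrolled in Aim 1 will be invited to" take part (section III.C, Insulin Discharge algorithm). The timing of the value is not stated.
- **Discharge bands.** The lower band, "Patients with an HbA1c between 7.0% and 10% will be discharged on preadmission oral" agents plus basal insulin, gives no timing. The upper band does: "Patients with an admission A1C ≥ 10" per cent.
- **Eligibility.** Exclusion criterion 2 (section IV) applies to diet-treated patients with an admission HbA1c below 7%. The matching inclusion criterion 3 gives no timing.
- **Hypothesis and analysis.** Section III.A expects that "treatment with degludec and glargine will result in a similar improvement in HbA1c" levels after discharge. Section VI.B lists the secondary outcomes as "rate of hypoglycemia during follow-up, change in HbA1c, body weight, number of episodes of" severe hyperglycemia, and so on. Adjustment is for unnamed potential confounders, chosen by stepwise, backward or forward selection. No HbA1c margin is given.

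**The concern.** A change score needs a defined starting point. Here it may be an admission draw in one patient and a chart value weeks older in the next. With an 11-week-old value, the 12-week change spans at least 11 + 12 = 23 weeks, nearly half of it before any study drug.

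Three things are at stake:

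- **Precision.** Drift between the chart date and admission enters the change score as noise. The plan offers tests of difference and no margin for HbA1c. If a non-significant difference is read as similarity, extra noise favours the hypothesis.
- **Within-arm improvement.** The hypothesis asserts improvement as well as similarity, and a before-after fall absorbs whatever happened before admission. Selecting patients at 7.0% or above on an old value also adds regression to the mean.
- **Consistency.** Two rules say admission HbA1c, while the footnote lets the recorded value be older.

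**Working it through.** **1. The plan's own figure.** Section VI.A sizes the trial on mean daily blood glucose: margin 18 mg/dl, SD 45 mg/dl, true difference 0, one-sided alpha 0.05, power 80%.

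n per group = 2 × (1.645 + 0.842)² × 45² / 18² = 77.3, so 78. This matches the plan. 78 / 0.87 = 89.7, so 90 per group agrees with the upper part of the 10–14% attrition range. Section VI.B reuses this for Aim 2. Nothing is sized on HbA1c, so nothing below changes a sample size, alpha or power figure.

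**2. Inputs for HbA1c.** From the documents (Rationale for study design, Aim 2), an earlier study saw HbA1c fall from 8.75% on admission to 7.35% at 12 weeks: 8.75 − 7.35 = 1.40 points. The documents give neither the share of chart values nor any drift, so these are assumptions:

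| Quantity | Assumed value |
|---|---|
| Share of chart values, f | 25–75% |
| Mean drift m (admission minus chart) | 0 to 0.5 points |
| Drift SD, d | 0.5–1.0 points |
| Admission HbA1c | mean 8.75%, SD 1.5–2.0 |

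**3. Within-arm offset.** Offset = f × m. The range is 0 to 0.75 × 0.5 = 0.375, about 0.38 points, or 0.375 / 1.40 = 27% of the earlier fall at most. If HbA1c rose before admission the fall is understated; if it fell, overstated.

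**4. Regression to the mean from selection at 7.0% or above on a chart value, mean drift zero.** Let c = √(SD² + d²) and a = (7 − 8.75)/c. The apparent fall is (d²/c) × φ(a) / [1 − Φ(a)].

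| Admission SD | d | c | a | Apparent fall |
|---|---|---|---|---|
| 1.5 | 0.5 | 1.581 | −1.107 | 0.04 |
| 1.5 | 1.0 | 1.803 | −0.971 | 0.17 |
| 2.0 | 0.5 | 2.062 | −0.849 | 0.04 |
| 2.0 | 1.0 | 2.236 | −0.783 | 0.17 |

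This applies to chart-value patients only; if they are half of the arm, the arm mean moves by half as much, 0.02–0.08.

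**5. Between-arm difference.** A two-arm simulation used 78 per arm, admission SD 1.75, and week-12 HbA1c = 7.35 + 0.4 × (admission − 8.75) + error with SD 1, with no treatment difference.

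- No chart values: standard error of the difference in change 0.237.
- f = 0.5 in both arms, m = 0.5, d = 1.0: bias −0.004, type I error 0.050, standard error 0.264. Ratio 0.264 / 0.237 = 1.11.
- f = 60% against 40%, same drift: bias 0.10 points in size, as (0.6 − 0.4) × 0.5 = 0.10 predicts.

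Analytic check: the variance of change is 0.6² × 1.75² + 1 = 2.1025. Chart values add f(d² + m²) − (fm)² = 0.625 − 0.0625 = 0.5625. The standard errors are √(2.1025 × 2/78) = 0.232 and √(2.665 × 2/78) = 0.261, which agree with the simulation to within about 2%.

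**6. What baseline adjustment recovers, same assumptions.** The variance of week-12 HbA1c is 0.4² × 3.0625 + 1 = 1.49, and its covariance with baseline is 0.4 × 3.0625 = 1.225.

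- Admission baseline: residual variance 1.49 − 1.225²/3.0625 = 1.00; standard error √(1.00 × 2/78) = 0.160.
- Half chart values: residual variance 1.49 − 1.225²/3.625 = 1.076; standard error √(1.076 × 2/78) = 0.166.

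So ANCOVA loses about 4% to the old values, where raw change loses 11–13%. Even with the noisy baseline it is more precise than raw change from a clean one (0.166 against 0.232). The size of that gain depends on the assumed slope of 0.4.

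**The case against.** The strongest reply is that the trial compares two randomized arms. Footnote 1 applies equally to both and a chart value precedes treatment, so drift cancels in expectation. That stands, and step 5 shows it. A reader might infer that pre-admission drift is mixed into the degludec–glargine effect; the documents do not support that. Aim 2 is an invited subset, so the share of chart values could differ by arm, but nothing in the plan makes this likely.

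A reader might also infer that Aim 2 entry, the discharge regimen and the hypothesis all require an admission value. The text does not say so: entry, the lower band and the hypothesis give no timing. Only the upper band and exclusion criterion 2 say admission. The title of the cited discharge algorithm and the 8.75% benchmark also refer to admission, but they are background, not rules of this trial.

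Third, the blank HbA1c cell at discharge might be read as a defect. It is not: a dated admission value would serve, and a discharge value would follow inpatient study treatment.

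Finally, the drift inputs are assumed, the 23-week example lies near the limit of what the footnote allows, and HbA1c is secondary. All of this is fair and limits severity. It does not answer the undefined baseline, the unnamed covariate or the inconsistent wording.

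**Conclusion.** The point holds as a minor one. The plan leaves the baseline for change in HbA1c undefined, permits a chart value under 3 months old, names no baseline adjustment, and refers to admission HbA1c in two rules without squaring that with the footnote.

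The consequence for the randomized comparison is lost precision, about 11% in standard error under the step 5 scenario. For each arm's own improvement it is an offset of 0 to 0.38 points in either direction, plus 0.04–0.17 points of regression to the mean in chart-value patients. These sizes rest on assumed shares and drift; the textual findings do not. Both primary endpoints and the sample size are untouched.

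**What to change.** 1. **Analysis (section VI.B).** Define the baseline HbA1c. Compare week-12 HbA1c between arms by ANCOVA with baseline HbA1c as a named covariate, in place of unadjusted change. This needs only wording.
2. **Measurement (footnote 1).** For patients who may enter Aim 2, take the analysis baseline from an index-admission sample drawn at or before the first study dose, not at discharge. Record the date and source of every baseline value. The cost is one routine HbA1c for patients who would otherwise use a chart value.
3. **Transfusion.** Flag transfused patients, since in-hospital values can be affected. This is the one small drawback of item 2.
4. **Where only a chart value exists.** Keep the patient and the value, and add a sensitivity analysis limited to admission-drawn baselines.
5. **Wording.** Reconcile the admission HbA1c in the upper discharge band and exclusion criterion 2 with footnote 1, and state the timing for Aim 2 entry and the lower band. No view is taken here on which value should guide the discharge regimen.

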550 achieve >80% power.

551
552 **Analysis of Primary Endpoint:** The primary endpoint in this study is glycemic control
553 measured by mean daily BG concentration after hospital discharge. Secondary outcomes include
554 rate of hypoglycemia during follow-up, change in HbA1c, body weight, number of episodes of
555 severe hyperglycemia, complications and emergency room visits or hospital readmissions at 12
556 weeks post-discharge. To analyze these outcomes, we will follow the same analytic strategy
557 proposed for the secondary endpoints of Aim 1. We will first compare the primary outcome
558 using two-sample t-tests (or Wilcoxon tests) or one-way ANOVA, followed by multivariate
559 linear regression to estimate and test the difference between the two treatment groups while
560 simultaneously accounting for other potential confounders. Transformations will be applied if
561 normality violation is detected. Stepwise, backward, or forward model selection strategy will be
562 adopted to determine the variables to be included in the final model. Standard diagnostic and
563 model checking procedures will be applied to examine the fit of the developed models.
564

565 **VII. DATA HANDLING AND RECORD KEEPING:**

566 Data collection records with personal identifiers will be stored in locked file cabinets. Blood
567 samples drawn in conjunction with this study will not be labeled with information that could
568 directly identify study subjects. Blood samples will be not be stored. Presentation of the study
569 results at regional or scientific meetings or in publications will not identify subjects. Access to
570 research and confidential records will be limited to clinical investigators, research coordinators,
571 and the IRB at Emory University.
572

573 **VIII. ETHICS:**

574 **Informed Consent.**

575 After identification of eligible patients these individuals will be provided basic information
576 regarding the study and, if interested, a member of the research staff using inclusion/exclusion
577 criteria delineated elsewhere in the protocol will then screen patients. Informed consent will be
578 obtained before any trial related procedures including screening procedures. The consent form,
579 potential risks and benefits, and the rights of research participants will be explained to the
580 participant by the investigators or research coordinator. Individuals will be asked if they have
581 questions, and a member of the research staff will answer questions. The principal investigator
582 (PI) will also be available at all times to answer questions that participants may have during the
583 consent procedure or during the time a participant is enrolled in the study. The consent form will
584 be completed only by trained research personnel familiar with the study protocol procedures,
585 informed consent process, who have undergone CITI training in accordance with the IRB
586 guidelines of Emory University. A signed copy of the consent form will be provided to the
587 participant and a copy will be placed in the file that is maintained for each participant in the
588 study office.

589 The study will be conducted in accordance with the Declaration of Helsinki and will be
590 conducted in accordance with the ICH GCP guidelines. The sponsor-investigator will comply
591 with all applicable regulatory and legal requirements, ICH GCP guidelines and the Declaration
592 of Helsinki in obtaining and documenting the informed consent.

593
594 **Recruitment Procedure.**

595 We screen all patients with hyperglycemia admitted to the hospital every day. Patients with
596 diabetes and hyperglycemia will be identified electronically following inclusion/exclusion
597 criteria. Once a potential candidate is identified, we will approach the primary team as well as

598 the patient and family for consent. We estimate that we will screen approximately 220-250
599 patients to analyze a total of 180 subjects, and expect to recruit about 2-4 patients per week”

600
601

602 **IX. STUDY SCHEDULE:**

FIRST PATIENT IN	DEC 2017
SCREENING	~220-250
ANALYZED	180
LAST PATIENT RECRUITED	MARCH 2020
LAST PATIENT IN	JUNE 2020
DATA ANALYSIS	AIM 1: 09/2020 ; AIM: 2: 12/2020
SUBMISSION TO CONGRESS OR JOURNAL	1/ 2021 (ADA); 4/2021: EASD

603

604 **X. STUDY DRUGS AND MATERIALS:**

605 **Study medication(s) / devices(s)**

606 Degludec insulin (U-100): 100 units/mL (U-100): 10 mL multiple-dose vial (1 vial per subject
607 during hospital admission): Inpatient arm: 90 patients. Total number of vials: 90

608 Degludec insulin 100 Units/mL, provided in 3 mL pen cartridges (outpatient arm).

609 Outpatient arm: 90 patients, average insulin dose: 30-45 U/day. Total number of cartridges: 100

610

611 Glargine insulin (U-100): 100 units/mL (U-100): 10 mL multiple-dose vial (1 vial per subject
612 during hospital admission): Inpatient arm: 90 patients. Total number of vials: 90

613 Glargine (U-100) insulin 100 Units/mL, provided in 3 mL pen cartridges.

614 Outpatient arm: 90 patients, average insulin dose: 30-45 U/day. Total number of cartridges: 100

615

616 Aspart insulin (U-100): 100 units/mL (U-100): 10 mL multiple-dose vial (1 vial per subject
617 during hospital admission): Inpatient arm: 180 patients. Total number of vials: 180

618 Aspart (U-100) insulin 100 Units/mL, provided in 3 mL pen cartridges

619 Outpatient arm: 180 patients, average insulin dose: 20-30 U/day. Total number of cartridges: 180

620 BG-Meters are considered standard of care and will not be provided.

621

622

623 **Packaging and Labelling of Study Medication(s)**

624 Degludec, aspart, and glargine will be stored and dispensed by the research pharmacy at each
625 institution. During the hospital stay (Aim 1) insulin will be kept at nursing stations and dosing
626 will be administered by nursing staff as per hospital protocol. Once dispensed and in use (after

627 first opening), insulin glargine can be stored for one month at room temperature (+15°C to
628 +30°C)/(59°F to 86°F) or in a refrigerator (+2°C to +8°C)/(+36°F to +46°F).

629 During the outpatient trial, all insulin prefilled pens \ will be stored in a refrigerator at a

630 temperature between +2°C and +8°C (+36°F and +46°F). Once dispensed and in use (after first
631 opening), insulin glargine can be stored for one month at room temperature (+15°C to

632 +30°C)/(59°F to 86°F) or in a refrigerator (+2°C to +8°C)/(+36°F to +46°F

633

634 **Drug accountability:** The trial product will be dispensed to each subject as required according
635 to treatment group. The research/clinical staff will perform drug accountability by asking
636 patients to return all unused, partly used and unused cartridges and vials of degludec and glargine
637 insulin at each visit.

638
639 **Randomization and Blinding**

640 This is an open label randomized multicenter controlled trial. Patients will be randomized
641 consecutively using a computer-generated randomization table provided by [name] at
642 the Emory School of Public Health. The randomization table will be mailed to the research
643 pharmacist at each institution who will be in charge of the randomization and group assignment.

644
645 **XI. CONCOMITANT ILLNESSES AND MEDICATIONS:**

646 **Definitions:**

647 During the hospital arm (Aim 1), all oral agents and insulin formulations will be discontinued at
648 randomization and patients will be treated as per study protocol with degludec/glargine as basal
649 bolus regimen with aspart as prandial insulin.

650 After discharge, patients will be treated with glargine or degludec insulin alone or in
651 combination with oral agents according to HbA1c levels.

652

653 **XII. ADVERSE EVENTS:**

654 **Definition:** An adverse event (AE) is any untoward medical occurrence in a subject
655 administered a product, and which does not necessarily have a causal relationship with this
656 treatment. An AE is an unfavorable and unintended sign (including abnormal laboratory
657 findings), symptom or disease temporally associated with the use of a product, whether or not
658 considered related to the product.

659 This includes events from the first trial related activity after the subject has signed the informed
660 consent and until post treatment follow-up period (telephone contact 2 weeks after last study
661 visit).

662 AEs include a clinically significant worsening of a concomitant illness and clinical laboratory
663 adverse event (CLAE). An AE is either a serious AE (SAE) or a non-serious AE.

664

665 The following AEs will be reported as an SAE using the important medical event criterion if no
666 other seriousness criteria are applicable:

- 667 - Suspicion of transmission of infectious agents via the trial product
- 668 - Risk of liver injury defined as alanine aminotransferase (ALT) or aspartate aminotransferase
669 (AST) >3 x UNL and total bilirubin >2 x UNL, where no alternative aetiology exists (Hy's law)
- 670 -Death
- 671 -A life-threatening event in which the subject was at risk of death at the time of the event
- 672 -Inpatient hospitalization and prolongation of existing hospitalization
- 673 -Persistent or significant disability or incapacity
- 674 -Important medical events that may not result in death, or a life threatening event but may
675 require hospitalization
- 676 -Episodes of severe hypoglycemia will be captured as serious AEs.
- 677 - A planned hospitalization for pre-existing condition, or a procedure required by the protocol,
678 without a serious deterioration in health, is not considered to be an SAE.

679
680
681
682
683
684
685
686
687
688
689
690
691
692
693
694
695
696
697
698
699
700
701
702
703
704
705
706
707
708
709
710
711
712
713
714
715
716
717
718
719
720
721
722
723
724

Severity Assessment Definitions:

- Mild: Transient symptoms, no interference with the subject’s daily activities
- Moderate: Marked symptoms, moderate interference with the subject’s daily activities
- Severe: Considerable interference with the subject’s daily activities, unacceptable

Relationship to Trial Product Assessment Definitions:

- Probable: Good reasons and sufficient documentation to assume a causal relationship
- Possible: A causal relationship is conceivable and cannot be dismissed
- Unlikely: The event is most likely related to an aetiology other than the trial product

Adverse events will be actively collected from the signing of the informed consent and in all following contacts throughout the project. This includes events from all trial related activity after the subject has signed the informed consent, and until the post treatment follow-up period, as defined in the protocol.

Outcome Categories and Definitions:

- Recovered: Fully recovered or by medical or surgical treatment the condition has returned to the level observed at the first trial related activity after the subject signed the informed consent
- Recovering: The condition is improving and the subject is expected to recover from the event. This term should only be used when the subject has completed the trial
- Recovered with sequelae: As a result of the AE, the subject suffered persistent and significant disability/incapacity (e.g. became blind, deaf, paralysed). Any AE recovered with sequelae should be rated as an SAE
- Not recovered
- Fatal
- Unknown

Reporting of adverse events: All events meeting the definition of an AE must be collected and reported. The events must be recorded in the AE form in a timely manner. During each contact with the trial site staff (site visits and telephone contacts), the subject will be asked about AEs. After the ICF is signed, all adverse events related to protocol procedures are to be reported. Suspected Unexpected Serious Adverse Reaction (SUSAR): An SAE which is unexpected and regarded as possibly or probably related to the trial/study product by the investigator. Serious adverse reaction (SAR): An Adverse event that fulfils both the criteria for a Serious Adverse Event and the criteria for an Adverse Reaction. An SAE report should be completed for any event where doubt exists regarding its seriousness. If the investigator believes that an SAE is not related to study drug, but is potentially related to the conditions of the study (such as withdrawal of previous therapy or a complication of a study procedure), the relationship should be specified in the narrative section of the SAE Report Form. SAEs, whether related or not related to study drug, and pregnancies must be reported to Emory IRB and Novo Nordisk by fax or email. SAEs must be recorded on an SAE Report Form or similar form (e.g. CIOMS, MedWatch). Within 15 days of becoming aware, the PI/sponsor will notify the FDA and all participating investigators via IND safety reports of events that are unexpected, caused by the study drug, and meet the FDA definition of “serious.”

725
726 **Reporting of pregnancies:** Female subjects who are pregnant or breast-feeding will not be
727 recruited in the study. Female subjects will be instructed to notify the investigator immediately
728 if they become pregnant during the trial. The investigator must report any pregnancy to the
729 Emory IRB and Novo Nordisk. The pregnant subject will be asked to provide information about
730 her pregnancy, delivery and the health of her infant until age one month. If the infant has a
731 congenital anomaly/birth defect this must be reported and followed up as a serious adverse event.

732
733 **Adverse events with additional data collection:** Adverse events with additional data collection
734 are those events thought to be [potentially] associated with the investigational compound or
735 disease under study. The investigators will collect information on medical events of special
736 interest including hypoglycemia, hyperglycemia (BG > 240 mg/dl), cardiovascular events (heart
737 failure, acute myocardial infarction, and atrial fibrillation), and medication errors (e.g., incorrect
738 dose of insulin).

739
740 **XIII. LIABILITY AND SUBJECT INSURANCE:**

741 **Financial Obligation.**

742 No additional cost to patients or to the institution will be incurred for research purposes. Patients
743 will not be billed for the laboratory work or any test that is being done only for study purposes.
744 Novo Nordisk will provide the study drugs (degludec, glargine and aspart insulin) at no cost to
745 participants. Patients will be responsible for the cost of their usual ongoing medical care,
746 including procedures and/or non-study medications that their doctor requires as part of their
747 usual medical care.

748
749 **Payment for Participation.**

750 Participation in this study is voluntary. Patients will receive one hundred dollars (\$100.00)
751 during the hospital stay and seventy- five dollars (\$75.00) after each clinic visit at 1 and 3
752 months after discharge. Total compensation will be two hundred and fifty dollars (\$250.00).

753
754
755 **Research Injuries.**

756 If a patient is injured because of taking part in this study, [name] and investigators at each
757 institution, along with the medical facilities will make medical care available. Emory University,
758 however, has not set aside any money to pay participants or to pay for their medical treatment.
759 The only exception is if it is proved that the injury or illness is directly caused by the negligence
760 of an Emory/Grady employee. “Negligence” is the failure to follow a standard duty of care.
761 Financial compensation for such things as lost wages, disability or discomfort due to an injury
762 related to the study is not available.

763
764 **XIV. Publication Plan:**

765 We anticipate completion of Aim 1 in September or October 2020 and Aim 2 in November 2020.
766 Data will be analyzed in December 2020 (aim 1) and in March 2021(aim 2). One abstract will
767 be submitted to the 2021 American Diabetes Association meeting and one to EASD 2021. Two
768 manuscripts will be submitted during the first six months of 2021.

769
770

771 **XV. References**

- 772 1. Umpierrez GE, Isaacs SD, Bazargan N, You X, Thaler LM, Kitabchi AE.
773 Hyperglycemia: an independent marker of in-hospital mortality in patients with
